#### **7.5.5      *Per-Protocol (PP) Analyses***

If at least 10% of total subjects in all treatment arms in the efficacy analysis population demonstrate relevant protocol deviations, a per-protocol analysis may be performed. A per-protocol analysis will be carried out for the primary and selected secondary endpoints (SRI (X): X = 4, 6.) based on the per-protocol (PP) analysis population. A Per-protocol (PP) analysis population will exclude all subjects with at least one relevant protocol deviation (defined in [Appendix 1](#)) from the efficacy analysis population based on the following rules.

- The subjects satisfying eligibility criteria deviation in [Appendix 1](#) will be excluded from the PP analysis population completely.
- The subjects satisfying incorrect dosing criteria deviation in [Appendix 1](#) will be excluded from the PP analysis population partially (only the data after deviation occurs will be excluded from the per-protocol (PP) analysis.)

### **7.6            *Safety***

Analysis of all safety data will follow the BMS standard safety data conventions  and supplements to the standard conventions as defined in this document.

The evaluation of drug safety is based primarily on clinical AE, laboratory abnormalities and vital signs reported during the study.

The summaries of AEs and laboratory marked abnormality during the ST period will be provided by treatment groups. AEs and laboratory marked abnormalities will be included in the summary tables based on ST period if the onset date is on or after the first dose date and event occurs

within the ST period for continuing subjects or within 42 days post last dose date for discontinued subjects.

Frequency distribution and individual listings of all AEs will be generated. Laboratory marked abnormality using pre-defined abnormality criteria will also be descriptively summarized. There will be no statistical testing of group difference with respect to frequencies of AEs or laboratory marked abnormalities.

All recorded adverse events will be listed and tabulated by system organ class, preferred term, treatment and overall. Any physical examination findings will be listed. ECG, vital signs and clinical laboratory test results and corresponding change from baseline values will be listed and summarized by treatment. Values for ECG, vital signs and clinical laboratory test results outside the pre-specified criteria will also be listed and summarized. ECG readings will be evaluated by the Investigator and abnormalities, if present, will be listed.

Unless otherwise specified, baseline is defined as the last non-missing result with a collection date-time less than the date-time of the first dose of study medication, for laboratory results, vital signs and ECG.

Presentations for the ST period will be provided by “as treated” treatment group for the as-treated analysis population, unless otherwise specified.

### **7.6.1 Adverse Events**

The investigator will determine the intensity of each AE as mild, moderate, severe, or very severe. In addition, the investigator will determine the relationship of the AE to the administration of the study drug.

All AEs are coded and grouped into Preferred Terms (PT) by System Organ Class (SOC), using the latest approved version of the Medical Dictionary for Regulatory Activities (MedDRA) at the time of database lock. Listings and summaries will be based on the resulting SOCs and PTs.

AEs will be included in the frequency tabulations if they occur while a subject is on study medication up to and including 42 days after the last dose of study medication. These AE summaries will be based on proportions, which represent the number of subjects experiencing the AEs divided by the number of subjects received with at least 1 dose of study medication in the current period.

All AE listings will indicate the unique subject identifier, age, gender, current treatment, the date of onset, the date of resolution, day of onset relative to the start of treatment, action taken, investigator’s assessment of severity and relationship to study drug. Additional listings will be provided for adverse events leading to discontinuation and adverse events without recorded resolution. Summaries of adverse events will include adverse events, adverse events by intensity and adverse events by relationship.

Where a subject has the same adverse event, based on preferred terminology, reported multiple times in a single analysis period, the subject will only be counted once at the preferred terminology level in adverse event frequency tables.

Where a subject has multiple adverse events within the same system organ class in a single analysis period, the subject will only be counted once at the system organ class level in adverse event frequency tables.

When a subject has the same adverse event, based on preferred terminology, reported multiple times in a single analysis period, the following criteria, in order of precedence, will be used to select the event to be included in summary tables:

- Relationship to study medication
- Intensity of event
- Onset date and time

When reporting adverse events by intensity, in addition to providing a summary table based on the event selection criteria detailed above, summary tables will also be provided based on the most intense event during the analysis period - independent of relationship to study medication. For these tables, the following criteria, in order of precedence, will be used to select the event to be included in summary tables:

- Intensity of event
- Onset date and time

Subjects will only be counted once in the 'Total' at their maximum intensity, regardless of SOC or PT.

Any reported AEs that occur more than 42 days after the last dose of study drug will be excluded from safety summaries. Any reported AEs that occur more than 42 days post the last dose of study drug will appear in the listing.

Summary information (the number and percent of subjects by treatment) will be tabulated for the following AEs:

- All AEs including clinical and laboratory AEs
- Most common AEs (reported in 5% of subjects or more in any treatment group)
- All related events
- Serious AEs (SAEs)
- Discontinuations due to AEs

Laboratory AEs are laboratory changes identified by the investigator as AEs and thus reported on the AE pages of the eCRF.

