- Interim analysis for futility and dose adaptation on BICLA response, SRI response, ACR28 and some SLE biomarkers (such as auto-antibodies, complement levels, etc.) with possible exploratory exposure response analysis, will be performed when approximately 30 subjects per arm have reached Study Day 85 (12 weeks), including subjects from Part 1 and Part 2, of treatment or have discontinued prior to reaching study Day 85. Analysis will be performed by an unblinded Sponsor team, while maintaining blind at the site and subject level. Based on the results, the dose levels and sample size may be modified.
- Ongoing assessment of safety will be performed by an independent Data Monitoring Committee (DMC) and an internal unblinded safety monitoring team. Both entities may make recommendations to the Sponsor regarding conduct of study and dose adjustment based on safety observations.

Following interim analyses and DMC reviews, dose arm(s) may be modified based on the results, as follows:

- If one or more arms are added, future randomizations will include the new arm(s).
- If one or more arms are dropped for safety reasons, randomization into that arm will be terminated and all subjects currently randomized to that or those arm(s) will be discontinued from receiving study medication.
- If one or more arms are dropped due to inadequate RO, there will be no new randomizations into that dose arm; subjects currently randomized may continue at the Investigator discretion.

The **long-term extension (LTE) period** is optional and will include eligible subjects who have completed Day 169 (week 24) of treatment and consent to participate. This period of the study will remain blinded but will no longer have a placebo arm. Eligible subjects will remain on their

originally-assigned dose arm, unless they were on the placebo arm during the short-term period. Placebo-arm subjects will be re-randomized into one of the existing active arms at Day 169 (24 weeks). Re-randomization of the placebo subjects will be done by IVRS and only the unblinded pharmacist/drug preparer will know the new randomization arm. The LTE will remain blinded to the study team and study personnel.

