3.2 Post Study Access to Therapy

At the time of writing there is no defined end date to the LTE period, however, the LTE provision may be further adjusted based on results from the ongoing lulizumab pegol development program. At the conclusion of the study, subjects who continue to demonstrate clinical benefit will be eligible to receive BMS supplied study drug. Study drug may be provided via an extension of the study, a rollover study requiring approval by responsible health authority and ethics committee or through another mechanism at the discretion of BMS. BMS reserves the right to terminate access to BMS supplied study drug if any of the following occur: a) the marketing application is rejected by responsible health authority; b) the study is terminated due to safety concerns; c) the subject can obtain medication from a government sponsored or private health program; d) BMS terminates development of the drug; or e) therapeutic alternatives become available in the local market.

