8.7.1.4 Safety Analyses

The evaluation of long term safety of the selected dose(s) will be based on clinical adverse events, vital signs and laboratory abnormalities reported during the LTE period. Frequency distributions and individual listings of all adverse events and laboratory marked abnormalities will be generated based on As Treated population. The results will be presented by treatment groups.

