## 2.4 Protocol Amendments

**Table 2.4-1: Protocol Amendments**

Amendment No.	Amendment Date	Main Purpose of Amendment
1	20-AUG-2014	Pharmacogenetics amendment
2	24-SEP-2014	Brazil specific amendment
3	16-DEC-2014	Japan specific amendment
4	11-FEB-2015	Argentina specific amendment
5	16-MAR-2015	Japan specific amendment to add Exclusion Criteria regarding Laboratory Test of Hepatitis-B and Allergies
6	28-APR-2015	Revised Protocol no.1 (adding LTE, allowing MMF, edits, adding clarity)
7	29-JUN-2015	Canada specific amendment to limit LTE to 1yr (until further data are available)
8	01-Oct-15	Removing RNA testing (Site 152 (Japan) only)
9	22-Apr-16	To add intensive PK blood sample collections and also add sparse receptor occupancy samples in the PK substudy

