## **6 STUDY PERIODS, TREATMENT REGIMENS AND POPULATIONS FOR ANALYSES**

### **6.1 Study Periods**

The following periods are defined in this SAP for the purpose of analyses and reporting.

**Pre-treatment period:** It covers the time period which starts from the day of enrollment and lasts until the initiation of the randomized double-blind treatment period.

**Short-term period (ST):** It starts at the time of the first dose of blinded treatment (BMS-931699 or placebo, regardless if it was received during Part 1 or Part 2 of study design) and continues up to the start of the first long-term extension dose (Day 169). For subjects who discontinue during the short-term period or do not enter the long-term extension period, it continues up to 42 days post last dose.

**Long-term extension period (LTE):** It starts at the first dose date of long-term extension (Day 169) and continues up to 42 days post the last study dosing date (LTE dose). Cutoffs may be applied for interim locks.

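### Short-term adverse-event tables show crude proportions without time at risk, so an arm stopped early for safety has its excess risk understated, and after a very early stop possibly reversed

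*SAP*

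**What the plan says.** **Measure.** SAP 7.6.1 says: "These AE summaries will be based on proportions, which represent the number of subjects experiencing the AEs divided by the number of subjects received". The same sentence gives the full denominator: "divided by the number of subjects received with at least 1 dose of study medication in the current period". It tabulates number and percent of subjects for all AEs, common AEs, related AEs, serious AEs (SAEs) and discontinuations due to AEs. The multiple-occurrence table (SAP 7.6.6) is also in numbers and proportions of subjects. Events of special interest are to be listed and summarised (SAP 7.6.2), with no person-time measure mentioned.

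**Counting window.** Under SAP 7.6, events count within the short-term period for continuing subjects, or "within 42 days post last dose date for discontinued subjects". SAP 6.1 ends the short-term period at the first LTE dose (Day 169). For subjects who discontinue or do not enter the LTE, "it continues up to 42 days post last dose".

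**Dropped arms.** If an arm is dropped for safety, "all subjects currently randomized to that or those arm(s) will be discontinued from receiving study medication" (Protocol 3.1, repeated in SAP 2.1). This can follow the Day 29 interim, the Day 85 interim (Rule 2) or a data monitoring committee (DMC) review. The As-Treated population (SAP 6.3) has no exclusion for dropped arms, so these subjects stay in the safety denominators.

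**Exposure.** SAP 7.4.1 tabulates days on drug, but no visible AE summary uses them. The time-to-event section (SAP 7.11.2) covers only treatment failure and flare.

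**LTE.** Protocol 8.7.1.4 says: "Frequency distributions and individual listings of all adverse events and laboratory marked abnormalities will be generated based on As Treated population". Protocol 3.2 adds: "At the time of writing there is no defined end date to the LTE period". SAP Table 2.4-1 records a "Canada specific amendment to limit LTE to 1yr". The LTE has no placebo arm, and analysis detail is left to a separate LTE SAP.

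**The concern.** A crude proportion compares arms fairly only if they are observed for similar lengths of time. Here the length can depend on the arm, and it is cut short in the arm about which there is a safety worry. The study report could then show that arm's AE, SAE or infection percentage close to placebo's, or below it, because its subjects had less time in which to have events. No between-arm testing of AEs is planned, but that is little protection, since readers compare the descriptive percentages directly. If time at risk is handled only after an arm has been stopped, the method will be chosen with the data in view.

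**Working it through.** **Inputs.** The planned timeline adds up as stated: 28 + 168 + 42 = 238 days (Protocol 3.1). The documents give no AE rate, so there is no AE figure to reproduce. The placebo risks and rate ratios below are assumptions.

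**Days counted from Day 1**
- Placebo subject entering the LTE: 168.
- Placebo subject not entering: weekly dosing with the first LTE dose at Day 169 puts the last short-term dose at Day 162, so 161 + 42 = 203 days (29 weeks). Counted from the end of treatment it is 168 + 42 = 210 days (30 weeks).
- Subject of a stopped arm with last dose on Day d: (d − 1) + 42.

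**Model.** Assume a constant hazard, including the 42 days off drug. If placebo risk is p0 over T0 days, an arm with rate ratio R counted for T1 days shows 1 − (1 − p0)^(R × T1/T0). This is below p0 whenever R < T0/T1, the break-even ratio.

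| All subjects' last dose | Days counted | Break-even v 168 days | Break-even v 203 days |
|---|---|---|---|
| Day 29 | 28 + 42 = 70 | 2.40 | 2.90 |
| Day 57 | 56 + 42 = 98 | 1.71 | 2.07 |
| Day 85 | 84 + 42 = 126 | 1.33 | 1.61 |

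**Doubled hazard, Day 29 stop, placebo 168 days.** With p0 = 20%: 1 − 0.8^(2 × 70/168) = 17.0%. Over a range of placebo risks, the stopped arm against placebo shows 4.2% v 5%, 8.4% v 10%, 17.0% v 20%, 34.7% v 40% and 63.3% v 70%. At 20% placebo risk, with 10 stopped and 70 placebo subjects, the stopped arm shows the lower percentage with probability 0.60, against 0.15 under equal follow-up.

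**Exposure-adjusted rate, same case.** Placebo: −ln(0.8)/168 × 36,525 = 48.5 per 100 patient-years. The doubled-hazard arm: 97.0. The ratio of 2 is recovered whatever the follow-up.

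**Later stop.** Take 18 weeks counted against 24, and R = 1.5.
- Placebo risk 60%: 1 − 0.4^(1.5 × 18/24) = 64% v 60%.
- Placebo risk 10%: 1 − 0.9^(1.125) = 11.2% v 10.0%.

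The excess keeps its direction but nearly vanishes: 64/60 is a crude ratio of about 1.07.

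**Staggered entry (assumed 2 to 6 subjects per arm per month).**
- Stop at the Part 1 interim: mean counted follow-up about 72 to 138 days, break-even about 1.2 to 2.3.
- Stop at the Day 85 interim: 138 to 155 days, break-even about 1.1 to 1.2. At 20% placebo risk, a doubled hazard then shows 30.2% to 33.4%, against 1 − 0.8² = 36% with full follow-up. That is dilution without reversal.

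**Opposite direction.** (d − 1) + 42 exceeds 168 once d is later than Day 127. A subject who stops late is therefore counted longer than a completer entering the LTE: by 203 − 168 = 35 days if the last dose is Day 162, or by 42 if counting starts from Day 169.

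**The case against.** The strongest reply is that reversal is a corner case. It needs an early stop or a modest rate ratio, and with staggered entry a stop at the Day 85 interim only dilutes a doubled hazard. This stands, and it limits the claim.

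A reader might infer that the arm closed for harm will generally look safer than placebo. The documents do not support that. It is tempting to give every placebo subject 30 weeks; the 18-week, 1.5-fold example then reverses (1 − 0.4^(1.5 × 18/30) = 56% v 60%). But SAP 6.1 and 7.6 stop counting at about Day 169 for LTE entrants, and the reversal needs mean placebo follow-up above 1.5 × 18 = 27 weeks. Most placebo subjects would have to decline the LTE. The bias can also run the other way.

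A reader might also extend the placebo contrast to the open-ended LTE. There is no placebo arm there. Entry date and the one-country cap are not specific to an arm; only dropping an arm makes follow-up differ by arm. The LTE SAP was not supplied, so nobody can say from these documents that it lacks a rate.

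Two further points are fair. The sponsor's standard safety conventions, which SAP 7.6 invokes, and the redacted sections were not available, so the statement covers visible text only. And the DMC and the unblinded safety team would already have found the harm, so the final table is not what detects it. That leaves the table's other purpose, describing the risk in the study report, and there the distortion remains. Exposure tables and onset days in listings let a careful reader suspect the problem but do not correct it.

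**Conclusion.** The point holds for the short-term period, conditional on an arm being dropped for safety. The visible AE tables are crude proportions, counted time then differs by arm, and nothing visible adjusts for it. Against 168 days of placebo follow-up, a common stop at Day 29, 57 or 85 reverses the crude comparison for true rate ratios below about 2.40, 1.71 or 1.33. Otherwise the usual result is an understated excess. These sizes rest on a constant hazard and assumed placebo risks; front-loaded events such as injection reactions would be less affected.

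For the LTE, the point is confined to comparisons among active arms and to the meaning of cumulative percentages. At one assumed rate of 0.3 per patient-year, 1 − exp(−0.3t) is 26% after one year and 59% after three. That contrasts follow-up lengths, not arms.

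**What to change.** In SAP 7.6.1 to 7.6.5, keep the crude tables and add exposure-adjusted incidence beside them: subjects with a first event per 100 patient-years at risk, with time running to the first event or the end of the counted period (including the 42 days where they apply), with 90% confidence intervals. Do this for all AEs, SAEs, events of special interest and discontinuations due to AEs. State in advance that, for any arm closed early, the comparison with placebo rests on this rate or on cumulative incidence at a common time. Carry the same rate into the LTE SAP if it is not already there.

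The cost is a few more tables from dosing and onset dates already collected. The rate assumes a roughly constant hazard, which is why it sits beside the crude percentage and why cumulative incidence is offered as the alternative. If an arm closes at the Part 1 interim with only 6 to 10 subjects, the rate will be imprecise: in the 17.0% example, 10 subjects give 1.7 expected with an event. The interval will show that.

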## **7.6.2 Adverse Events of Interest**

The following adverse events of special interest will be listed and summarized by treatment groups during the ST period.

- Infections: All reported infections and infestations within the SOC: *Infections and infestations*. The severity of serious infections will be summarized. In addition, a listing of opportunistic infections will be provided.
- Malignancy: All reported events defined in MedDRA Maintenance and Support Services Organization (MSSO) Structured MedDRA Query (SMQ) list.
- Autoimmunity: All reported events defined in pre-specified MedDRA code of autoimmune disorders.
- Injection Reactions (Local and Systemic): All reported events defined in pre-specified MedDRA code of injection reactions (Local and Systemic).

### **7.6.3 Deaths**

All AEs with the outcome of death reported during the study will be listed. All reported deaths after a subject is enrolled will be listed separately by subject.

### **7.6.4 Other Serious Adverse Events**

SAEs are captured on an eCRF page. All SAEs and related SAEs will be summarized by treatment group and listed.

### **7.6.5 Adverse Events Leading to Discontinuation of Study Therapy**

AEs leading to discontinuation of study drug are identified on the eCRF will be listed and summarize.

### **7.6.6 Multiple Occurrences of Adverse Events**

Several descriptive summaries of adverse events that takes into account the number of occurrences that an AE was reported by individual patients will be provided. In order to prepare these summaries, the CRF data will be processed according to standard BMS algorithms to categorize each line of patient data as a new occurrence or a continuation of an existing event. This determination will be based upon onset and resolution dates. Each line of patient data will represent the maximum severity observed as well as the last known assessed relationship to study medication by the investigator.

The number and proportion of subjects who experienced an AE once or multiple times (0 Events, 1 Events, 2-3 Events,  $\geq 4$  Events) will be summarized by treatment groups for most common AE (at least 5% subject in any treatment group) and event of special interest, infections.

Listing displaying the unique instances of all AEs will be provided.

Note: The unique instances of all AEs will be generated after duplicates have been eliminated and overlapping and contiguous occurrences of the same event have been collapsed.

### **7.6.7 *Summaries of Laboratory Data***

The results of all protocol-specified clinical laboratory tests, as well as laboratory results outside of the normal range, will be listed. Scheduled laboratory measurements and corresponding change from baseline values will be summarized by treatment and nominal visit for each laboratory test for the MITT analysis population.

The frequency of subjects with any marked laboratory abnormality (based on sponsor defined criteria) will be presented by laboratory test during the ST period. The results are based on the As-treated analysis population. The criteria used for classifying laboratory test results as markedly abnormal will be listed.

